Appendix B. Statistical Analysis to Account for Impact of COVID-19 Pandemic

1.0 Overview

The COVID-19 pandemic is interfering with the conduct of many ongoing trials, with potential impacts on treatment duration and collection, analysis and the interpretation of clinical trial data. Some protocol-specified visits in the clinical trials may be impacted due to COVID-19 infection or logistical restrictions during the pandemic. For example, some scheduled visits may be missed due to self-quarantine or local government restrictions on travel; some visits may also be delayed or canceled due to healthcare resource constraints during the pandemic. Impacted visits due to COVID-19 will be recorded in the database.

This appendix describes the additional analyses and updates to existing analyses due to COVID-19 impact. At the time of COVID-19 pandemic, all study subjects are in Period 2 of the study. The primary efficacy analysis and Period 1 reporting have been completed in 2018 and are not affected by the COVID-19 pandemic. The analyses described in this appendix are only applicable to Period 2 and future reporting of the long term analyses.

2.0 Patient Disposition

Period 2 patient disposition and reason for discontinuation will be summarized as described in Section 7.0. For subjects who prematurely discontinued study drug or study participation, the reasons for discontinuation will be summarized with two additional categories capturing discontinuation due to COVID-19 infection or logistical restrictions related to the COVID-19 pandemic (as collected in CRF):

- Adverse event (AE)
- Withdrew consent
- Lost to follow-up
- Lack of efficacy
- COVID-19 infection
- COVID-19 logistical restrictions

- Other

In addition, the number and percentage of subjects with scheduled study visits affected by COVID-19 pandemic will be summarized by treatment group sequences. The impact on study visits will be summarized by the following categories (as collected in CRF) by visit:

- Missed visit
- Virtual visit
- In person, partial assessments done

3.0 Long Term Efficacy Analysis

Missing data could occur due to various reasons, including missing visits/assessments, early withdrawal from the study, or missing due to COVID-19 infection or logistic restriction. The probability of having missed visits and missing data due to COVID-19 infection or logistical restrictions related to the COVID-19 pandemic can be reasonably assumed to be unrelated to the unobserved values. Therefore, for the purpose of statistical analysis, it is reasonable to assume that these missing data are missing at random (MAR) and the statistical models that require MAR assumption are appropriate.

As described in Section 9.4, longitudinal analysis models MMRM and GLMM will be used for long term efficacy analysis for the "non-switcher" treatment sequences, and will be maintained for long term efficacy analysis in the presence of missing data due to COVID-19.

4.0 Safety Analysis

In listings of adverse events and deaths, a flag indicating whether the event or death was related to COVID-19 infection will be presented. A listing of COVID-19 related adverse events may be provided.

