**Figure 5. Adverse Event Collection**

Additionally, in order to assist the adjudication process, additional information on any potential cardiovascular events including thromboembolic events will be collected, if applicable.

In case of any of the following reported events, an appropriate supplemental eCRF should be completed:

- Cardiac events;
- Myocardial infarction or unstable angina;
- Heart failure;
- Cerebral vascular accident and transient ischemic attack;
- Cardiovascular procedures (SAE Supplemental Procedure eCRF);
- Embolic and thrombotic events (non-cardiac, non-CNS);
- Hepatic;
- Renal;
- Herpes Zoster Infection;
- CPK increase considered by the investigator to be an AE.
- COVID-19.

Supplemental study case report forms should be completed in the event of COVID-19 related missed/virtual visits, study drug interruptions or discontinuations, or adverse

events (including documentation of specific signs/symptoms of infection and testing results).

COVID-19 infections should be captured as adverse events. If the event meets the criteria for a serious adverse event (SAE), then follow the SAE reporting directions per the protocol and above.

The following COVID-19 related supplemental eCRFs should be completed (for both serious and non-serious events):

- COVID-19 Supplemental Signs/Symptoms
- COVID-19 Status Form

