Subjects could be blindly switched from Upadacitinib monotherapy to the combination of upadacitinib + MTX at Week 26, or could have background csDMARD added/initiated after Week 26, depending upon the CDAI response and joint counts. For subjects rescued with blinded study drug MTX at Week 26, the exposure under upadacitinib monotherapy is censored prior to the day when blinded study drug MTX is initiated. For subjects not rescued with blinded study drug MTX at Week 26 but added/initiated csDMARD as a background therapy, the exposure under the monotherapy of upadacitinib is censored prior to the day when the first dose of csDMARD is initiated.

Starting with Amendment 5.01.01 (for Japan) and Amendment 6 (for global), subjects receiving upadacitinib 30 mg QD will be switched to receiving upadacitinib 15 mg QD. Exposure to upadacitinib 30 mg QD (Groups 4 and 5) will be censored prior to the day subject received the first dose of upadacitinib 15 mg QD, and subsequent exposure to upadacitinib 15 mg QD will be summarized under separate groups (Groups 6 and 7).

The duration of exposure to study drug will be summarized for each group as specified above, with the number of subjects, mean, standard deviation, median, minimum and maximum values. In addition, the number and percentage of subjects exposed to study drug will be summarized for the following cumulative duration intervals.

- ≥ 2 weeks
- ≥ 1 month
- ≥ 3 months
- ≥ 6 months
- ≥ 9 months
- ≥ 12 months
- ≥ 18 months
- ≥ 2 years
- ≥ 2.5 years
- ≥ 3 years
- ≥ 4 years

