10.2.1.6 Adverse Events of Special Interest

The Adverse Events of Special Interest (AESI) categories will be summarized and presented by "as treated" treatment group and overall using SOC and MedDRA PT. The AESI categories will be identified per Standard MedDRA Queries (SMQs)/Company MedDRA Queries (CMQs) in [Table 12](#) below. Adjudicated cardiovascular events will be summarized and presented by treatment group using the CAC adjudicated categories.

Table 12. AESI for Upadacitinib with SMQs/CMQs/PTs Searches

AESI	Type of MedDRA Query	Broad or Narrow Search	SMQ/CMQ Search Criteria
Serious Infections	CMQ		"Infections" – Subset for SAEs
Opportunistic Infection excluding Tuberculosis and Herpes Zoster	CMQ		"Opportunistic Infection excluding Tuberculosis and Herpes Zoster"
Possible Malignancy	SMQ	Narrow	"Malignancies"
Malignancy	SMQ		"Malignant tumours"
Non-Melanoma Skin Cancer (NMSC)	SMQ	Narrow	Skin Malignant tumours (Narrow SMQ) removing Melanoma CMQ
Malignancy excluding NMSC			"Malignant tumours" SMQ removing NMSC output
Lymphoma	SMQ		"Malignant Lymphomas"
Hepatic Disorder	SMQ	Narrow	"Drug Related Hepatic Disorders"
Adjudicated Gastrointestinal Perforations	Output from adjudication		
Anemia	CMQ		"Non-Hemolytic and Non-Aplastic Anemias"
Neutropenia	CMQ		"Hematological Toxicity – Neutropenia"
Lymphopenia	CMQ		"Hematological Toxicity – Lymphopenia"
Herpes Zoster	CMQ		"Herpes Zoster"
Creatine Phosphokinase (CPK) Elevation	PT		Search only for the PT of "Blood creatine phosphokinase increased"
Renal Dysfunction	SMQ	Narrow	"Acute Renal, Failure"
Active Tuberculosis	CMQ		"Active Tuberculosis"
Adjudicated Cardiovascular Events	Output from CAC		
MACE*			
Cardiovascular Death			
Non-fatal Myocardial Infarction			
Non-fatal Stroke			

Table 12. AESI for Upadacitinib with SMQs/CMQs/PTs Searches (Continued)

AESI	Type of MedDRA Query	Broad or Narrow Search	SMQ/CMQ Search Criteria
Undetermined/Unknown Cause of Deaths			
Other Cardiovascular events			
Adjudicated Thrombotic Events	Output From CAC		
Venous Thromboembolic Events**			
Deep Vein Thrombosis			
Pulmonary Embolism			
Other Venous Thrombosis			
Arterial Thromboembolic Events (non-cardiac, non-neurologic)			

CAC = Cardiovascular Adjudication Committee; CMQ = company MedDRA query; PT = preferred term; SMQ = standard MedDRA query

* MACE; Major Adverse Cardiovascular Events, defined as cardiovascular death, non-fatal myocardial infarction and non-fatal stroke.

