10.2.2 Analysis of Long Term Adverse Event Rates

Long term adverse event rates will be analyzed using event rates adjusted by cumulative exposure and will be based on the actual treatment received at the time of AE occurrence. Starting with Amendment 5.01.01 (for Japan) and Amendment 6 (for global), subjects receiving upadacitinib 30 mg QD will be switched to upadacitinib 15 mg QD. For these subjects, adverse events and exposure to upadacitinib 30 mg QD will be censored at the time of dose switch; subsequent adverse events and exposure starting the day of first dose

of upadacitinib 15 mg QD will be summarized under separate groups. The detailed treatment exposure groups, including the handling of dose switch, are described in Section 8.1.

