10.2.2.1 Overview of Adverse Events Rates per 100 Patient-Years of Study Drug Exposure

An overview of AEs per 100 patient-years of study exposure will be presented by treatment group and overall for the following AE categories.

- All TEAEs
- Treatment-emergent serious adverse events (SAEs)
- Treatment-emergent severe adverse events
- TEAEs reasonably possibly related to study drug
- TEAEs of special interest
- TEAEs leading to discontinuation of study drug
- TEAE leading to death

For this calculation, one year will be considered to be 365.25 days. For each treatment group, the numerator of the overall rate will be the total number of TEAEs reported for the event; that is, a subject can contribute more than one event to the numerator. For each treatment group, the denominator of the rates will be the total number of days exposed to study drug summed across all treated subjects divided by 365.25. The TEAE rate per 100 patient-years of exposure will be calculated as $(\text{[numerator/denominator]}) * 100$. The number of TEAEs reported (numerator), the total number of years of study drug exposure (denominator), and the TEAE rate per 100 patient-years will be presented for each treatment group and overall.

In the AE overview summary, any event with an unknown severity will be considered as severe and any AE with an unknown relationship will be considered as having "reasonable possibility" of being related to study drug. Additional TEAEs may be

considered for tabulation/summary based on recommendations from Clinical and Safety as deemed appropriate.

For TEAEs of special interest, the point estimate and 95% CI (using normal approximation) will be provided for the treatment difference in the TEAE rate per 100 patient years between each Upadacitinib dose group and the MTX group.

As a sensitivity analysis, the AE overview summary per 100 patient-years of study exposure will be repeated by exposure groups. In this summary, all AEs with an onset date after the first dose of study drug will be included, regardless of whether the AE occurred more than 30 days after the last dose of study drug. This sensitivity analysis will only be performed in final CSR.

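### Long-term adverse event rates keep COVID-19 events in, while 30 mg exposure stops at about the time the pandemic begins and MTX exposure runs on, so the planned rate differences versus MTX are confounded with calendar time

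*SAP*

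**What the plan says.** Protocol 6.1.4 requires that "COVID-19 infections should be captured as adverse events". SAP 10.2.2 analyses long-term events by the treatment received when the event occurred. In SAP 10.2.2.1, "the numerator of the overall rate will be the total number of TEAEs reported for the event", and "the denominator of the rates will be the total number of days exposed to study drug summed across all treated subjects divided by 365.25". The same construction serves the tables by system organ class and preferred term (10.2.2.2) and those for events of special interest (10.2.2.3). In SAP Table 12, serious infections are the company infections query with the restriction "Subset for SAEs". The table has no COVID-19 row or exclusion.

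On the dose switch, SAP 8.1 states: "Exposure to upadacitinib 30 mg QD (Groups 4 and 5) will be censored prior to the day subject received the first dose" of 15 mg. From that point, "subsequent adverse events and exposure starting the day of first dose" of 15 mg go to separate groups (Groups 6 and 7). No such cut applies to MTX monotherapy (Group 1) or to subjects on 15 mg throughout (Groups 2 and 3).

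SAP 10.2.2.1 commits to a point estimate and 95% confidence interval, for events of special interest, for the rate difference between each upadacitinib dose group and MTX.

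Appendix B 4.0 has two provisions: "In listings of adverse events and deaths, a flag indicating whether the event or death was related to COVID-19 infection will be presented", and "A listing of COVID-19 related adverse events may be provided". Neither changes a rate.

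**The concern.** An exposure-adjusted rate can be compared across groups only if the background hazard is similar over the time each group contributes. Here the 30 mg patient-years end at roughly the point where a new infectious hazard appears. The MTX and continuous 15 mg patient-years lie on both sides of that point, and the post-switch 15 mg patient-years lie almost entirely after it. COVID-19 events are counted wherever they fall.

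The 30 mg groups therefore carry few of these events per patient-year, MTX carries some, and the post-switch groups carry most. The difference in serious infection between 30 mg and MTX is pushed in favour of 30 mg, and post-switch 15 mg is pushed the other way. SAE and death rates, shown side by side, are affected in the same manner. Long-term safety is a stated Period 2 objective, and infection is where a JAK inhibitor's rates are read most closely.

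**Working it through.** The plan states no figure to reproduce, so the check measures how far calendar time and exposure group overlap.

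**From the documents**
- Amendment 6: 16 December 2019. Amendment 5.01.01 (Japan): 15 July 2019 (Protocol 1.1).
- Japan supplies 37 of the 300 subjects in the 30 mg arm.
- Period 2 visits are 12 weeks apart to Week 240, and the last is at Week 260.
- All subjects had reached the end of Period 1 by September 2018 (Protocol 5.5.5.2). Subtracting 337 days puts the last first doses at about October 2017.

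**Assumed**
- First doses spread uniformly from February 2016 to October 2017.
- Local approval 1, 3 or 6 months after the amendment, then a switch at the next 12-weekly visit.
- Pandemic onset on 1 January, 1 March or 1 July 2020.
- No attrition, and follow-up to Week 260.
- A COVID-19 event rate c per 100 patient-years of pandemic time, equal in all groups (no drug effect).

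**Formula**

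Spurious difference (A − B) = c × (pandemic share of A's exposure − pandemic share of B's exposure).

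**Central case: 3-month lag, onset 1 March 2020 (decimal years)**
- Mean first dose 2016.916. Course 260 × 7 / 365.25 = 4.983 years, so mean end 2021.899. Onset 2020.164.
- Mean switch = amendment date + 0.25 + half of 12 weeks (0.115). This gives 2020.320 outside Japan and 2019.899 in Japan. Weighted by 263/300 and 37/300, it is 2020.269.
- MTX or continuous 15 mg share: (2021.899 − 2020.164) / 4.983 = 34.8%.
- 30 mg: exposure 2020.269 − 2016.916 = 3.35 years. Pandemic part 0.877 × (2020.320 − 2020.164) = 0.137, with nothing from Japan. Share 4.1%.
- Post-switch 15 mg: exposure 2021.899 − 2020.269 = 1.63 years. Pre-pandemic part, Japan only, 0.123 × (2020.164 − 2019.899) = 0.033. Pandemic share 98.0%.
- With c = 3: 30 mg − MTX = 3 × (0.041 − 0.348) = −0.92. Post-switch 15 mg − MTX = 3 × (0.980 − 0.348) = +1.90.

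**Range over the assumptions, from simulation (c = 3; differences per 100 patient-years)**

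| Lag, onset | 30 mg share | MTX share | Post-switch share | 30 mg − MTX | Post-switch − MTX |
|---|---|---|---|---|---|
| 3 months, 1 Mar | 4.1% | 34.8% | 98.0% | −0.92 | +1.90 |
| 1 month, 1 Mar | 0.7% | 34.8% | 95.4% | −1.02 | +1.82 |
| 6 months, 1 Mar | 10.0% | 34.8% | 99.7% | −0.75 | +1.95 |
| 6 months, 1 Jan | 14.4% | 38.1% | 100.0% | −0.71 | +1.86 |
| 1 month, 1 Jul | 0.0% | 28.1% | 77.9% | −0.84 | +1.50 |
| 6 months, 1 Jul | 1.9% | 28.1% | 96.6% | −0.79 | +2.06 |

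The differences scale with c. For the serious-infection row, c is the rate of serious COVID-19 only. If that is 0.5 to 2 (assumed), the share differences above give −0.12 to −0.68 for 30 mg and +0.25 to +1.37 for post-switch 15 mg.

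**Sensitivity to the no-attrition assumption.** SAP 8.1 censors MTX monotherapy at rescue to combination therapy, which lowers its late exposure. If the MTX share were 20% instead (assumed), the central-case differences would be 3 × (0.041 − 0.20) = −0.48 and 3 × (0.980 − 0.20) = +2.34. The 30 mg difference vanishes only if the MTX share falls to that of 30 mg.

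**After the change.** With COVID-19 events removed, c = 0 and both differences are 0. Within one calendar period, all groups have the same pandemic share, and the differences are again 0.

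**The case against.** The strongest reply is that the planned tables already expose COVID-19. SAP 10.2.2.2 and 10.2.2.3 give rates by preferred term with numerators and patient-years. If COVID-19 codes to its own terms, a reader can subtract it. Appendix B also lists COVID-19 infection as a discontinuation reason, and the SAP allows further tabulations. This partly stands: the information is not hidden. But the tables commit to no difference versus MTX without these events and no interval for one. Subtraction by term may also miss events that the relatedness flag would identify under another term.

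A reader might infer that the tables will make 15 mg look worse than 30 mg in the same subjects. The documents do not support that reading. No contrast of 30 mg with post-switch 15 mg is planned. Groups 4 and 5 include subjects who stopped before the switch, whereas Groups 6 and 7 hold only those still on drug. With an assumed background serious-infection rate of 3 per 100 patient-years and 0.5 to 2 from COVID-19, the ratio would be 3.5/3 to 5/3, or 1.17 to 1.67. If the survivors' background were 2 (assumed), it would be 2.5/3 to 4/3, or 0.83 to 1.33. The direction is not determined, and that comparison would not be a dose effect even without a pandemic. A calendar split cannot rescue it, because the two groups barely overlap in time.

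Two further cautions hold. The contents of the company infections query are not shown, although nothing in the SAP removes COVID-19 from it. Missed or virtual visits could reduce reporting of other events during the pandemic, so the net direction in the overall event rates is likely rather than certain.

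**Conclusion.** The concern holds for the planned differences versus MTX in events of special interest, chiefly serious infection, and for the SAE and death rates read across groups. Over the assumptions tried, 0% to 14% of 30 mg exposure falls in the pandemic, against 28% to 38% for MTX or continuous 15 mg and 78% to 100% for post-switch 15 mg. At 3 COVID-19 events per 100 patient-years, 30 mg appears 0.7 to 1.0 per 100 patient-years below MTX, and post-switch 15 mg 1.5 to 2.1 above it, with no drug effect. The sizes depend on assumed onset, switch timing, attrition and event rates. The mechanism follows from the SAP's own definitions.

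A reader might also infer that the trial's main conclusions are at risk. They are not: SAP 11.1 and Appendix B 1.0 state that the primary efficacy analysis and Period 1 reporting were already complete. This is a should-fix for long-term safety reporting only.

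**What to change.** Keep the planned rates and add to SAP Appendix B 4.0, with cross-references from 10.2.2.1 to 10.2.2.3:

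1. Supplementary rates with COVID-19-related events excluded, using the flag already planned, for all TEAEs, SAEs, severe events, events leading to discontinuation, deaths and the infection events of special interest. Repeat the differences versus MTX and their 95% confidence intervals on the same basis.
2. For the infection and death rows, events and patient-years of every exposure group split at one calendar date fixed before database lock. The 30 mg groups can then be compared with MTX and continuous 15 mg before the pandemic, and post-switch 15 mg with MTX and continuous 15 mg during it.
3. A sentence stating that the split does not make 30 mg and post-switch 15 mg comparable with each other.

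The cost is SAP wording and a few repeated tables. Protocol 6.1.4 already provides the COVID-19 case report forms, so no new data are needed.
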